9.6.5 Physical Measurements

The baseline physical measurements (height (cm), weight (kg), BSA (m²)) and the change from baseline of weight and BSA will be summarized by cycle for each treatment arm.

9.6.6 Electrocardiogram

The electrocardiogram (ECG) measurements from this clinical study were performed as per standard of care for routine safety monitoring, rather than for purposes of assessment of potential QTc effect. ECG data might be presented in listings.

9.6.7 Left Ventricular Ejection Fraction (LVEF)

LVEF (assessed by ECHO) and the change of LVEF from baseline will be summarized using descriptive statistics by treatment arm by visit.

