Secondary	
PFS over the duration of the study: Kaplan-Meier (KM) estimates for PFS distribution by treatment and PFS rates and CI at 6 and 12 months, stratified Cox proportional hazards (PH) model for HR and CI estimate. The synthesis approach will be used to show that once-weekly KRd 56 mg/m^2 preserves at least 50% of twice-weekly KRd 27 mg/m^2 effect vs Rd.
 
Patient-reported convenience after cycle 4 of treatment: Cochran-Mantel-Haenszel method will be used to evaluate the treatment effect (OR) for whether carfilzomib dosing is reported as convenient or inconvenient; a logistic regression model including the randomization stratification factors and treatment group will be considered for sensitivity analysis
 
Time to response: mean, SD, median, minimum and maximum among responders.
 
Duration of response (DOR): KM method among responders.
 
Time to progression (TTP): KM method and stratified Cox PH model.
 
OS over the duration of the study: KM estimates for OS distribution by treatment and OS rates and CI at 6 and 12 months, stratified Cox PH model for HR and CI estimate.
 
MRD[-]CR: proportion of MRD[-]CR will be reported with CI calculated using Clopper-Pearson method.
 
MRD[-] status at 12 months from randomization: proportion of MRD[-] will be reported with CI calculated using Clopper-Pearson method.
 
Physical functioning and role functioning (EORTC QLQ-C30) over time: repeated measures analysis of covariance adjusting for the baseline covariates. A restricted maximum likelihood-based mixed model for repeated measures (MMRM) will be considered as sensitivity analysis.
 
Patient-reported treatment satisfaction (CTSQ) after cycle 4 of treatment: analysis of covariance at the corresponding fixed time point.

Exploratory	Will be described in the statistical analysis plan finalized before database lock.

Safety analyses will be based on the safety population (defined as all randomized subjects who have received at least 1 dose of any study treatment [carfilzomib, lenalidomide, or dexamethasone]). The number and percentage of subjects experiencing 1 or more adverse events will be summarized by treatment group, relationship to study treatment, and severity. Changes from baseline and shift in toxicity grade in safety laboratory test results, left ventricular ejection fraction and vital signs will

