be summarized using descriptive statistics. Adverse events and safety laboratory test results will be graded for severity using the National Cancer Institute Common Terminology Criteria for Adverse Events (NCI-CTCAE) Version 5.0.

Subjects' demographics and disease characteristics, in addition to prior and concomitant medications and study treatment exposure, will be summarized descriptively for each treatment group.

[figure not shown]
For a full description of statistical analysis methods, please refer to Section 10.

Sponsor Name: Amgen Inc.

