## 2.2 Schedule of Activities

**Table 2-1. Schedule of Activities**

PROCEDURE	Screening a (up to 28 days before random)	Treatment Period Cycles 1 to 12							Safety FU (30 [+3] days after last dose)	LTFU b (every 28 ± 7 days)	Notes
		Day 1	2	8	9	15	16	22			
GENERAL AND SAFETY ASSESSMENTS											
Informed consent	X										
Inclusion and exclusion criteria	X										
Demographics	X										
Medical history	X										Including multiple myeloma history
Substance use	X										Tobacco only
Complete physical examination	X							X			
Physical measurements	Height	X									
	BSA	X	(X)								BSA should be calculated during screening per Mosteller formula and utilized to calculate required study drug doses. BSA should be recalculated if weight changes by more than 20% (gain or loss) from weight used at the most recent BSA calculation.
	Weight	X	X								
12-lead ECG with QTc interval		X		(X)							Screening and as clinically indicated.
	cycle 1			X							To be performed at the end of carfilzomib infusion
	cycle 2		X								
Vital signs (once-weekly arm)	X	X	X	X	X			X			Checked prior to administration of carfilzomib in all cycles. In cycles 1 and 6, an additional blood pressure measurement post-carfilzomib infusion will be collected (within 30 minutes of the end of infusion).
Vital signs (twice-weekly arm)	X	X	X	X	X	X	X				
ECOG performance status	X							X			
Echocardiogram	X	(X)							X		During treatment every 6 months (± 2 weeks) from C1D1 until SFU and additionally as clinically indicated. An ECHO must be performed within 72 hours of the onset of a suspected cardiac failure event.

Page 1 of 8

Footnotes are defined on the last page of the table.

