**Table 7-3. Dose Modification Guidelines for Nonhematologic Toxicities**

Symptom/Sign/Investigation	Recommended Action
Congestive heart failure	Any subject with congestive heart failure, whether or not drug-related, must have the dose held until resolution or return to baseline. Appropriate medical management should be initiated and continued as clinically indicated. If no resolution after 4 weeks, carfilzomib will be permanently discontinued.
	< Grade 3 Once congestive heart failure resolves or returns to baseline, resume at full dose.
	≥ Grade 3 Once congestive heart failure resolves or returns to baseline, treatment may continue at 1 dose level reduction.
Infection (grade 3 or 4)	Hold carfilzomib. Once infection is controlled and the subject is without infection-related symptoms, and if ANC > 1.0 × 10  /L, resume at full dose. If ANC < 1.0 × 10  /L, follow hematologic toxicities dose reduction guidelines.
Hepatitis B reactivation	Hold carfilzomib until infection is adequately controlled (see Section 9.2.3.4.3).
Neuropathy (grade 2 with emergent pain, or grade 3)	Hold carfilzomib until resolved to ≤ grade 2 without pain; then resume at 1 dose decrement.
Neuropathy (grade 4)	Permanently discontinue carfilzomib.
Dyspnea (grade ≥ 2)	Hold carfilzomib until resolution to grade 1 or baseline, then resume at 1 dose decrement. Investigate cause and record findings. If caused by another adverse event listed in this table, follow recommendations for that adverse event.
Hypertension (SBP > 140 and/or DBP > 90, measured per Appendix 10 in Section 12.10)	
< grade 3	Continue at same dose and initiate appropriate treatment to control hypertension (see Section 12.10 for guidance)
	Grade ≥ 3 Hold carfilzomib until resolution to normal or baseline. Initiate appropriate antihypertensive therapy prior to resuming carfilzomib at 1 dose decrement.
Pulmonary toxicity: Non-infectious interstitial lung disease, acute respiratory failure, ARDS (≥ grade 3)	Hold carfilzomib until resolution to grade 1 or baseline and restart at 1 dose decrement.
Pulmonary hypertension (grade ≥ 3)	Hold carfilzomib until resolution to grade 1 or baseline and restart at 1 dose decrement

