#### **9.2.3.4 Other Safety**

##### **9.2.3.4.1 Echocardiogram**

All subjects will have a baseline ECHO, including assessments of systolic and diastolic left ventricular function and right ventricular function. Screening ECHO may be done within 30 days prior to randomization, if performed as a part of standard of care.

Echocardiogram is to be repeated approximately every 6 months ( $\pm$  2 weeks) from cycle 1 day 1 until safety follow-up visit, and additionally, if clinically indicated. An ECHO must be performed within 72 hours of the onset of a cardiac failure event.

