9.1 General Considerations

Where applicable, descriptive statistics will be provided. For continuous variables, the number of subjects with non-missing data (n), mean, standard deviation (STD), median, minimum, and maximum will be presented. For categorical variables, the frequency (n) and percentage will be summarized in each category. The denominator for percentages is the number of subjects in the analysis set of interest for the summary. The binomial proportions and the corresponding 95% confidence intervals (CIs) will be based on the exact distribution methods (Clopper-Pearson interval) and the treatment comparison will be based on Cochran-Mantel-Haenszel (CMH) method. Time to event endpoints will be estimated using the Kaplan-Meier (KM) method and will be summarized with the number of subjects with events or censored, and censoring reasons, KM quartiles (when estimable) and corresponding two-sided 95% CIs, KM proportions at select time points, inferential comparison between treatment arms with associated p-values, hazard ratios from stratified Cox proportional hazard (PH) model, and KM curves.

The analyses of efficacy and safety endpoints will be based on the analysis sets defined in [Section 6](#). The primary (final) analyses of the efficacy endpoints and Patient-report outcomes will use the ITT population, while the Per Protocol Set will be used for sensitivity analyses, if applicable. The analyses of the safety endpoint will be based on the safety population.

The primary analysis of ORR and PFS will be based on IRC assessed outcomes. The synthesis approach will be used to show that KRd 56 mg/m² QW preserves at least 60% of KRd 27 mg/m² BIW effect vs Rd in terms of ORR and 50% in terms of PFS. The null hypotheses for the primary and key secondary objectives (ORR, PFS, and convenience after cycle 4 of treatment) will be tested using a fixed sequence hierarchical testing procedure to control the family-wise type I error rate at 1-sided 0.025 level. The testing is ordered as follows: non-inferiority of ORR, non-inferiority of PFS, and superiority of patient-reported convenience after cycle 4 of treatment. Starting with the hypothesis of ORR, if any null hypothesis in the sequence is rejected, then the subsequent hypothesis

will be tested. Otherwise, if any hypothesis failed to be rejected, then the subsequent hypotheses will not be tested. For all other endpoints, the significance testing, if performed, will be considered descriptive.

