9.6.3 Laboratory Test Results

Laboratory test results will be graded for severity using the NCI-CTCAE version 5.0 and will be summarized for each treatment arm using descriptive statistics for baseline values and changes from baseline values by cycle (per table 2-1 from protocol), and a summary of subject incidence of grade 3 and 4 laboratory abnormalities.

For the summary of changes from baseline values, subjects without a baseline and/or post-baseline value will be excluded; values from unscheduled assessments will not be included. Laboratory results from samples taken > 30 days after the last administration of protocol therapy will be excluded from all laboratory summaries.

Shifts in laboratory toxicity grades to outside the normal range will be evaluated for laboratory parameters by assessing the maximum increase and/or decrease observed

during the course of study treatment relative to the baseline toxicity grade. The following selected laboratory parameters may be considered in this analysis.

- (1) hematology analytes in decreasing direction: Hemoglobin, Lymphocyte, Absolute Neutrophil Count (ANC), Platelet, White Blood Cell (WBC);
- (2) chemistry analytes in increasing direction: Alanine Aminotransferase (ALT), Aspartate Aminotransferase (AST), Total Bilirubin, Corrected Calcium, Serum Creatinine, Potassium, Sodium, Magnesium, Uric Acid;
- (3) chemistry analytes in decreasing direction: Albumin, Corrected Calcium, Potassium, Magnesium, Phosphorus, Sodium.

The subject incidence of Grade 3 and 4 hematological laboratory abnormalities and the subject incidence of Grade 3 and 4 nonhematological toxicities (including liver function test (LFT), creatinine) will be provided by treatment arm in the same table.

The summary table for ALT, AST, Total Bilirubin, and the potential Hy's Law cases will also be considered.

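### The LVEF grade shift in the protocol synopsis is missing from SAP 9.6.7, and no planned summary counts subjects by their worst ejection fraction

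*SAP*

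**What the plan says.** The protocol synopsis (Statistical Considerations) states that "Changes from baseline and shift in toxicity grade in safety laboratory test results, left ventricular ejection fraction and vital signs will" be summarized descriptively; the sentence runs over a page break. Read as written, both the change and the grade shift apply to all three measures.

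SAP 9.6.7 consists of one sentence: "LVEF (assessed by ECHO) and the change of LVEF from baseline will be summarized using descriptive statistics by treatment arm by visit". SAP 9.1 defines descriptive statistics for continuous variables as n and mean together with "standard deviation (STD), median, minimum, and maximum will be presented". Grade shifts appear in SAP 9.6.3 only: "Shifts in laboratory toxicity grades to outside the normal range will be evaluated for laboratory parameters by assessing the maximum increase and/or decrease observed". SAP Section 10 lists three changes from the protocol (the RMST analysis and the retention rate for PFS, and the ORR margin) and does not mention LVEF.

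On timing, Table 2-1 of the protocol schedules echocardiograms at screening and then "During treatment every 6 months (± 2 weeks) from C1D1 until SFU and additionally as clinically indicated", and marks one at the safety follow-up visit. Protocol 9.2.3.4.1 adds that "An ECHO must be performed within 72 hours of the onset of a cardiac failure event".

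**The concern.** Protocol 3.3.3 names cardiac failure as a key identified risk of carfilzomib. Section 3.3.3.1.1 counts decreased ejection fraction within it and says that events arise throughout therapy. The trial is open-label, so adverse event reporting can be influenced by knowledge of the arm. LVEF is the one direct measure of cardiac function that the SAP summarizes by arm after baseline: NT-proBNP is taken at screening only, and SAP 9.6.6 leaves ECG data to possible listings.

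Two things are missing from the planned LVEF analysis. The grade shift announced in the synopsis has gone without being declared. And the echocardiograms most likely to show a fall, those triggered by symptoms or by a cardiac failure event, have no stated place in a table laid out by visit. At stake is whether the clinical study report can say how many subjects per arm had a material fall in LVEF.

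**Working it through.** The plan gives no figure for this analysis, so there is none to reproduce. The check compares the texts and then illustrates sensitivity.

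**1. Promise against plan**

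| Measure | Protocol synopsis | SAP |
|---|---|---|
| Laboratory tests | change and grade shift | change and grade shift (9.6.3) |
| LVEF | change and grade shift | values and change by visit (9.6.7) |
| Vital signs | change and grade shift | values and change by cycle (9.6.4) |

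The LVEF shift is absent and not declared in SAP Section 10. The vital-sign shift is absent in the same way.

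**2. Where a triggered echocardiogram would go**

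Twelve cycles of 28 days are 336 days, about 11 months at the SAP's 30.4 days per month. A subject who completes treatment without delay therefore has about two scheduled post-baseline echocardiograms: near month 6 and around safety follow-up. SAP 9.6.3 and 9.6.4 say that unscheduled values are left out of their change-from-baseline summaries. SAP 9.6.7 says nothing: it neither excludes triggered echocardiograms, nor assigns them to a visit, nor feeds them into a worst-value summary. The handling is left to programming.

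**3. How far a by-visit mean can move**

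Inputs from the documents: 230 subjects per arm (protocol 5.2); all-grade cardiac failure of 7.1% in the KRd arm of ASPIRE, and of 3.8% once-weekly and 5.1% twice-weekly in A.R.R.O.W., which used a different once-weekly dose and no lenalidomide (protocol 3.3.3.1.1). Assumptions, not in the documents: each affected subject loses 10 to 20 LVEF points, all at the same visit and all captured in the table; the SD of LVEF is 6 to 10 points.

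- Expected subjects = 230 × rate: 230 × 0.071 = 16.3; 230 × 0.051 = 11.7; 230 × 0.038 = 8.7.
- Movement of the arm mean = rate × fall: at 7.1%, 0.71 to 1.42 points; at 3.8%, 0.38 to 0.76 points.
- SE of the difference between arms = SD × √(2/230): 0.56 points at SD 6, 0.75 at SD 8, 0.93 at SD 10.
- With the A.R.R.O.W. rates in the two arms, the difference in means is (0.051 − 0.038) × 10 to 20 = 0.13 to 0.26 points, below half of even the smallest of these SEs.

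These assumptions favour the by-visit table, since every fall is taken as visible at one visit. The minimum in the table shows only the single lowest value per arm and visit. None of the planned statistics says how many subjects fell, or by how much.

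**The case against.** The case on the other side has several parts, and some of them stand.

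- **The harm is reported elsewhere.** This stands. Clinically significant abnormal assessments are adverse events under the protocol's Appendix 4. SAP 9.6.2 tabulates treatment-emergent events overall, at grade 3 or higher, serious, fatal, leading to discontinuation, and as events of interest. A cardiac failure event that triggers an echocardiogram is itself counted. A reader might infer that the plan hides cardiac harm; the documents do not support that. The SAP does not name cardiac failure as an event of interest, but the general tables do not depend on that.
- **It is not only a mean.** This stands. LVEF itself is summarized as well as its change, with median, minimum and maximum.
- **Triggered echocardiograms are not excluded.** This stands as to wording. A reader might infer exclusion from the laboratory and vital-sign sections, but 9.6.7 carries no such sentence. The fault is an unstated rule.
- **Affected subjects need not have recovered by the next echocardiogram.** Table 7-3 says that "Any subject with congestive heart failure, whether or not drug-related, must have the dose held until resolution or return to baseline", from which a reader might infer that scheduled values will look normal. But subjects who stop treatment still have a safety follow-up visit with an echocardiogram. In the ASPIRE KRd arm, 2.6% were stabilized or not resolving and 0.5% resolved with sequelae, out of 7.1%: (2.6 + 0.5) / 7.1 = 44%. Adverse event outcome is not LVEF, but the figure argues against assuming recovery.
- **The promise is thin.** This stands in part. It appears in the synopsis only, protocol 10.3.2.3 has no LVEF subsection, and the grading sentence names other data: "Adverse events and safety laboratory test results will be graded for severity using the National Cancer Institute Common Terminology Criteria for Adverse Events". So LVEF grading was never specified. That is a reason to name the grading or declare the omission, not to leave the two documents at odds.
- **Unscheduled echocardiograms depend on suspicion.** This stands. Unblinded investigators order them, so a worst-value table can reflect how often each arm was examined. Scheduled echocardiograms are less exposed to this, which is why the by-visit table should stay.

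**Conclusion.** The point holds as a gap in safety reporting. The synopsis commits to a grade shift for LVEF, SAP 9.6.7 does not deliver it, and SAP Section 10 is silent. The planned summary is insensitive to a fall in a few percent of subjects and has no stated place for the triggered echocardiograms, so it adds little to the adverse event tables. It has no effect on type I error, power or the primary analysis.

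The textual part needs no assumptions. The sensitivity part rests on assumed LVEF falls and SDs; the cardiac failure rates come from earlier trials. The direction does not depend on exact values, because a fall in a few percent of subjects is diluted by the rest of the arm.

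A reader might go further and compare the power of a by-visit mean with that of a count of affected subjects. The documents do not support such a comparison: SAP 9.6.7 plans no test, and the result would depend on an invented difference between arms and on how many falls each table is assumed to catch. At the A.R.R.O.W. rates the expected counts are about 9 and 12 subjects, so the added table would describe the falls rather than settle a difference.

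**What to change.** In SAP 9.6.7:

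1. Keep the by-visit table and state that it uses scheduled echocardiograms.
2. Add a table of worst post-baseline LVEF per subject over all echocardiograms, scheduled and unscheduled, up to the safety follow-up visit. Show the shift from baseline grade, naming the grading used, and n (%) per arm by size of the maximum fall from baseline, with the bands fixed before database lock.
3. Report the number of scheduled and unscheduled echocardiograms per subject by arm beside it, so that uneven examination is visible.

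If the sponsor prefers not to restore the shift, SAP Section 10 should declare the omission; the vital-sign shift can be settled in the same edit.

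The cost is one table and a short rule, from data already collected, with no change to conduct. SAP 9.6.3 already uses the maximum change for laboratory shifts, so the approach is not new to the plan. The remaining downside is the dependence of unscheduled echocardiograms on clinical suspicion. The counts in item 3 disclose this but do not remove it.

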9.6.8 Exposure to Investigational Product and Non-Investigational Products

Descriptive statistics will be produced to describe the exposure to all study drugs (carfilzomib, lenalidomide, and dexamethasone) by treatment arm for subjects in the Safety Analysis Set. The extent of exposure will be evaluated, where applicable, with respect to the following:

- Number of treatment cycles subject dosed

For all study drugs, it is defined as the total number of treatment cycles in which at least one dose of any study drug is administered. For each study drug (carfilzomib, lenalidomide, dexamethasone), it is defined as the total number of treatment cycles in which at least one dose of carfilzomib/lenalidomide/dexamethasone, respectively, is administered.

- Number of subjects dosed in each cycle for all study drugs and each study drug
- Treatment duration (week): $(\text{last dose date} - \text{first dose date} + 1) / 7$

For all study drugs, the last/first dose date refers to the last/first dose date of any study drug. For carfilzomib/lenalidomide/dexamethasone, the last/first dose date refers to the last/first dose date of carfilzomib/lenalidomide/dexamethasone, respectively.

- Number of doses administered (non-zero dose) of each study drug during the treatment period of the study
- Cumulative dose received (mg, mg/m²) of each study drug during the treatment period of the study, defined in [Section 5](#).
- Average dose per administration (mg, mg/m²) of each study drug during the treatment period of the study, defined as the total cumulative dose received divided by the number of doses administered.
- Average dose per administration (mg, mg/m²) excluding the 20 mg/m² of carfilzomib on cycle 1 day 1 and/or day 2 during the treatment period of the study, defined as the total cumulative dose received divided by the number of doses administered.
- Relative dose intensity of each study drug defined in [Section 5](#).

- The number (%) of subjects with dose modifications of each study drug will be tabulated and the reasons for dose modification will also be summarized. If the reason for dose modification is COVID-19 control measures which is recorded in the specified field (Other) on the CRF, then the number (%) with COVID-19 control measures will also be presented.

Dose modifications will include the following:

[figure not shown]
- Dose missed (for each study drug, derived based on the Carfilzomib/ Lenalidomide/Dexamethasone Investigational Product Administration CRF)
- Dose reduction (each study drug, derived based on the Carfilzomib/ Lenalidomide/Dexamethasone Investigational Product Administration CRF)
- Dose delay (for carfilzomib only, as captured on the Investigational Product Administration (Carfilzomib) CRF)
- Dose interruption (for carfilzomib only, as captured on the Investigational Product Administration (Carfilzomib) CRF)

The primary reason for study drug discontinuation will be summarized along with the summary of subject disposition ([Section 9.2](#)).

